## Protocol Synopsis

### *Brief Summary*

We will conduct a parallel-arm, double-blind individually randomized control trial (RCT) in 30 healthy older adults, where attentional control demands in working memory training will be systematically increased using engaging game-based simulations. There are three parallel arms. The first two arms use experimenter-designed simulation games, where participants will be trained on either predictable low attentional control (Arm 1: Low-C) or unpredictable high attentional control (Arm 2: High-C) working memory games. The third arm uses a commercially-available strategy video game requiring highest level of attentional control (Arm 3: High-C+), by adding multi-tasking to the unpredictable attentional shifts in working memory. In all three training arms, neural and cognitive changes in both near and far tasks will be examined immediately after the 8-week long intervention. Long-term cognitive changes will also be assessed at 6 months after completion of training. The far and near cognitive domains that will be examined in this RCT are episodic memory (the primary cognitive outcome, and a marker of early stages of AD) and executive control (the secondary cognitive outcome). We expect that the high attentional control training arms will greatly improve both primary and secondary cognitive outcomes in older adults not only immediately after the training, but also at the +6-month period. We also expect cognitive frailty to interact with the extent to which attentional control is trained.

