### **Study Design**

**Overview.** This parallel arm, individually randomized control trial (RCT) will recruit 34 older adults from Dallas and neighboring counties. We aim to retain at least 30 participants on whom immediate post-training gains in both *near* and *far* abilities can be observed. This RCT shall be registered at [ClinicalTrials.gov](https://clinicaltrials.gov). There will be a Clinical Coordination Team (co-directed by [name] and the Project Manager) that will implement the intervention and check in with the participants on a weekly basis regarding their training progress. A blinded data collection team, directed by a post-doctoral fellow, will collect both behavioral and neuroimaging assessments before and after training. There will also be

a Data Coordination Team (co-directed by [name] and a post-doctoral fellow) that will be responsible for scoring and preprocessing the data. All data will be deposited in a HIPAA compliant server at the PI's laboratory. The team leaders will meet twice a month and each team will meet weekly to oversee any issues with subject recruitment, logistics and data collection. We will also recruit a total of 20 younger adults (YA, 18-30 years of age) for neuroimaging, who will be the functional controls for the older adults in the RCT.

This is a Phase 1 trial with multiple interventions in older adults, where the goal is to compare high attentional control trainings (High-C and High-C+) to low attentional control training (Low-C) and evaluate training-related changes in neurocognitive functions of both near (secondary outcome) and far transfer (primary outcome) tasks.

***Experimental Design.*** There are three intervention arms for older adults (OA) in this RCT trial, where attentional control demands in working memory training will be systematically increased using engaging game-based simulations.

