If after the pre-screening and the Mock Scan sessions, a volunteer meets the inclusion and exclusion criteria, he or she will be randomized into one of the three training arms. This assignment will be based on a random computerized allocation plan, where the average cognitive frailty, age, education and gender distribution will be maintained to be equivalent across the three arms. By randomly assigning participants in the training arms and by assessing outcomes by blinded experimenters, we will avoid selection bias and outcome assessment bias. The power analyses for sample size justification, therefore, is for this individual randomized trial, where Type 1 and type II errors are defined, expected meaning difference between the experimental groups and Low-C are specified, and attrition is estimated at follow ups. The participant will need to be randomized to a training arm prior to any baseline assessments.

***Minimizing Attrition and Enhancing Adherence.*** Attrition at follow ups will be minimized because in addition to the weekly in-lab training, there will be weekly at-home training where the participants can conduct the training from the comfort of their home during their preferred time on the device (Windows tablet) provided to them. Compliance for at-home sessions will be measured by the device's time stamp, which will be recorded every time the participant logs into the training program. Participants will also be provided with a diary to keep a log of their training schedule to enhance compliance. Moreover, participants will be encouraged to call researchers of the unblinded, training group with any questions about the game. The weekly in-lab testing will ensure that any difficulties participants may encounter during at-home training is resolved.

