***Sample Size Justification for the older adults in the RCT.*** We estimated the power (using G\*power3.1) to detect the differences between the Training Arm (3) x Assessment (2) interaction on the primary cognitive outcome. *The current study is the first phase of a larger randomized controlled trial. We calculate our power for the full trial, but our requested sample size for this study is 51.* We will recruit 177 older adults with the aim to retain a total sample size of 144 older adults at immediate post-training with the expected attrition of 18%. We report two expected effect sizes of Cohen's *f* for our calculations. One,  $f=.35$ , the minimum effect size obtained across our 3 pilot studies. Another,  $f=.16$ , based on a meta-analysis on computer-based cognitive training in older adults. The proposed total sample size of 144 older adults will provide us with >93% power to detect the Training Arm (3: Low-C, High-C, High-C+) x Assessment

(A vs. B) interaction at  $f=.16$  and  $>98\%$  power to detect the interaction at  $f=.35$  on the primary cognitive outcome at  $p<.05$ . It will also provide  $>90\%$  power to detect a meaningful between-group difference ( $f=.35$ ) at immediate post-testing, after controlling for baseline cognition, at  $p<.05$ . At +6mo retention period (Assessment C), we expect to retain a total of 117 older adults, after the expected  $\sim 20\%$  attrition between Assessments B and C. This will provide us with  $>87\%$  power to detect the Training Arm (3: Low-C, High-C, High-C+) x Assessment (2: A vs. C) interaction at  $p<.05$  at  $f=.16$ . We will conduct 2 ANOVAs, one for primary and one for secondary. Our proposed sample size will provide us with sufficient power ( $>87\%$ ) to detect the Training Arm (3) x Assessment (2) interaction at a corrected  $p$  value of .025 ( $=.05/2$  for 2 cognitive outcomes of interest).

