### **Data Analysis Plan**

All data will be initially tested for normality, outliers, and errors. We will then compute summary statistics and derive across-group statistical comparisons to identify any demographic variables, such as age, gender, education, or cognitive frailty, group differences after the randomization process. If group differences are detected for a variable, all analyses will include that variable as a covariate. We will also present primary and secondary outcome measures using descriptive statistics, summarize categorical variables using frequencies and proportions, and report descriptive statistics as medians and interquartile ranges.

***Analyses of Primary and Secondary Cognitive Outcomes.*** Outcomes will be tested according to the intention-to-treat principle with analysis of variance, evaluating both the changes from baseline to the completion of training (immediate treatment effects) and the changes from baseline to +6mo after training (retention effects). All analyses will be conducted on the baseline-normed Blom transformed scores for each measure, an approach used in prior intervention research on older adults. Composite cognitive scores (for each cognitive outcome) will be formed by averaging these scores. Therefore, we shall conduct all statistical analyses on one composite cognitive score representing the primary outcome (episodic memory) and one composite score representing the secondary outcome. There will be, for both outcomes, three composite scores- one for each Assessment (A, B and C). Specific Aim 1 focuses on the increases in cognition between the three training arms at both immediate post-testing and +6mo period. Change scores for each composite score for each individual will first be plotted to evaluate the treatment-related cognitive benefits. We will then examine the composite scores for the primary outcome using repeated measures ANOVA, with Training Arms (3: Low-C, High-C, High-C+) as a between-subject factor and Assessment (2) as a within-subject factor, for both immediate post-training gains (Assessments A and B) and for long-term retention of these gains (Assessments A and C). Of main

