interest is the interaction between the Training Arms and Assessments. To evaluate the extent of immediate post-test cognitive gains across the three training arms, we will conduct pairwise contrasts between High-C and High-C+. Similar analysis will be conducted for the secondary outcome. The two ANOVAs will be adjusted to  $p < .025$  ( $= .05/2$ ) to adjust for multiple comparisons.

Additional analyses will investigate how *cognitive frailty*, as measured by MOCA and MMSE, interacts with training difficulty (High-C vs. High-C+) and extent of transfer, because cognitively fit older adults show faster learning rates for complex skills and working memory. We predict that older adults with greater cognitive frailty will exhibit less cognitive plasticity and therefore will benefit most from moderate attentional control training (High-C), whereas older adults with higher cognitive functioning will find the most challenging training dose (High-C+) to be most beneficial and exhibit greatest cognitive plasticity.

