***Analyses of Primary and Secondary Neuroimaging Outcomes.*** There are two main fMRI tasks of interest- one for primary cognitive outcome (episodic memory), called *subsequent memory*; another for secondary cognitive outcome (executive control), called *task-switching*. An additional fMRI task, *working memory updating*, a near transfer task for all arms, will also be evaluated. For each task, we will derive a summary BOLD measure that best characterizes neural activity for the task after correcting for multiple comparisons. Those summary values will be entered into an ANOVA, where the Training Arm (3: Low-C, High-C, High-C+) x Assessment (pre-test vs. post-test) interaction will be evaluated, followed by post-hoc analyses of these interaction effects. We will also calculate group differences in the contrasts of interest at the post-test scans. The critical contrasts of interest for the subsequent memory is Remembered vs. Forgotten items, and for task-switching is Dual vs. Single task. The resulting ROI clusters, after correcting for multiple comparisons, will be used to extract percent signal change for all individuals at both pre-test and post-test. Specific Aim 2 evaluates whether the post-training changes in fronto-parietal activations are largest in the High-C and High-C+, compared to the Low-C, training arms. The percent signal change data will be submitted to a Training Arm x Assessment ANOVA, which will be followed by planned-comparisons between the groups to evaluate the specific aim 2. These interaction effects will be conducted for all task difficulty conditions in the fMRI tasks, because post-intervention activation patterns are hypothesized to be different for simpler conditions (e.g., 0-back; Single task; water present) compared to the more difficult conditions (e.g., 3- back, Dual task; water absent) of the fMRI tasks. We will also calculate task-specific activations for difficult vs. simpler condition contrasts (e.g., 3-back>0-back; Dual>Single; water absent>water present) in younger adults (YA), after correcting for multiple comparisons. The resulting ROI

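### The cognitive analysis names High-C versus High-C+ as its only follow-up contrast, so the comparison with Low-C that defines the trial's goal is not pre-specified at either time point

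*Combined protocol and SAP*

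**What the plan says.** The Study Design overview states that "the goal is to compare high attentional control trainings (High-C and High-C+) to low attentional control training (Low-C"). In the Data Analysis Plan, "Specific Aim 1 focuses on the increases in cognition between the three training arms at both immediate post-testing and +6mo period". The Brief Summary expects the High arms to improve cognition "not only immediately after the training, but also at the +6-month period".

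For the cognitive composites, the plan specifies a repeated measures ANOVA with three arms and two assessments, run once for A and B and once for A and C. The arm-by-assessment interaction is the effect of main interest. The only follow-up then stated is: "To evaluate the extent of immediate post-test cognitive gains across the three training arms, we will conduct pairwise contrasts between High-C and High-C" (High-C+ is the second arm). The secondary composite is to be handled in the same way. The .025 level is attached to the two ANOVAs; no level is given for the contrasts.

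Three other places come close to a Low-C contrast without stating one for cognition:

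- Screening and Randomization says that the "expected meaning difference between the experimental groups and Low-C are specified", but gives no test.
- The Sample Size Justification claims "power to detect a meaningful between-group difference" at immediate post-testing, adjusted for baseline. It does not name the arms, and the analysis plan does not take it up.
- The neuroimaging section has an ANOVA "which will be followed by planned-comparisons between the groups to evaluate the specific aim 2". That is for imaging.

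**The concern.** The interaction has 2 numerator degrees of freedom. Rejecting it shows that the three mean changes are not all equal. It does not show that either High arm gained more than Low-C, and it could be significant because Low-C gained most.

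The one contrast that would follow leaves Low-C out. If both High arms beat Low-C by the same amount, which would fulfil the synopsis expectation, its true difference is zero. If it does reject, it shows that the two High arms differ from each other, which still says nothing about Low-C. At +6 months no follow-up contrast is stated at all.

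Followed as written, the plan therefore answers the question in its own goal statement only through descriptive statistics and plots, or through a contrast that it did not commit to beforehand.

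**Working it through.** **1. Stated tests, cognitive composites**

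| Question | Immediate (A to B) | +6 months (A to C) |
|---|---|---|
| Any difference in change among the arms (2 df) | stated | stated |
| High-C versus High-C+ | stated | not stated |
| High-C versus Low-C | not stated | not stated |
| High-C+ versus Low-C | not stated | not stated |

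The cognitive frailty analysis also names only High-C and High-C+. Comparisons involving Low-C appear only for imaging: the Aim 2 planned comparisons, and the ANOVA of Low-C, High-C+ and younger adults.

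**2. Reproducing the plan's power**

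For the within-between interaction in the G*Power metric, λ = f²·N·2/(1−ρ), with 2 and N−3 df. The documents give no correlation ρ. With ρ = .5 and f = .16:

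- N = 144: λ = .0256·144·2/.5 = 14.75. Power at .05 is 93.5% (stated: above 93%).
- N = 117: λ = 11.98. Power is 87.4% (stated: above 87%).

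So ρ = .5 fits the sponsor's own calculation. These figures are for the full trial and for the interaction only; no power is stated for any named pair of arms.

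**3. What the contrasts can show in this study**

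Inputs: 30 retained (Study Design), taken as 10 per arm; f = .16 and .35 (Sample Size Justification). Assumptions: ρ = .5; the .025 level used for contrasts as well as ANOVAs; every contrast two-sided, with pooled variance, and tested only after a significant interaction. Change-score SD is set to 1.

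- λ = .0256·30·4 = 3.07 for f = .16, and .1225·30·4 = 14.70 for f = .35. The interaction rejects in 20% and 85%.
- λ = 10·Σ(arm mean change − overall mean change)² fixes the size d of the gain:
  - Equal gains (0, d, d) or one High arm only (0, 0, d): λ = 10·(2/3)·d², so d = .679 and 1.485.
  - Graded gains (0, d, 2d): λ = 20·d², so d = .392 and .857.

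Simulated rejection rates, f = .16 / f = .35:

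| Pattern of gains | High-C vs High-C+ (named) | At least one Low-C contrast |
|---|---|---|
| Equal | 2% / 2.5% | 20% / 85% |
| Graded | 6% / 34% | 19% / 85% |
| One High arm only | 15% / 78% | 16% / 79% |

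Over ρ from .3 to .7 and all three patterns, the last column runs over 11–35% / 61–98%.

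The Sample Size Justification gives 51 as the requested sample. If 51 are recruited and its 18% attrition applies, 51·.82 ≈ 42 remain (14 per arm), and the equal-gain figure for at least one Low-C contrast is 30% / 96%.

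A larger sample does not rescue the named contrast. At N = 144, f = .16 and equal gains, without the gate, it still rejects in 2.5%, while each Low-C contrast rejects in about 85%.

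**4. Is the error rate affected?**

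Take three arms, with pairs tested at .025 only after the interaction is significant at .025. If all arms are equal, the interaction is falsely significant in 2.5%. If exactly two are equal, only one pair is a true null, and it is tested at .025. If all differ, no false rejection is possible. Any pair is therefore protected for that outcome and time point, even one that was not named beforehand.

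**The case against.** The strongest reply is that this is a first-phase trial feeding a larger one, and that Low-C and +6 months already sit inside the tests of main interest. The named sentence speaks of gains across three arms and uses the plural for contrasts, so Low-C was probably lost in drafting. All of this is fair, and it makes the correction easy. It does not put the contrasts into the plan: no section states them for cognition.

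A second reply is that an unplanned Low-C contrast after a significant interaction would do no harm. Step 4 shows that this is right for the error rate within one outcome and time point. A reader might infer that the plan inflates type I error here; that inference does not hold. What stands is that the plan does not commit to which contrast, at what level, or behind what gate.

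A third reply is that the goal could equally be met by one contrast of the pooled High arms against Low-C. The wording allows it. Ungated at .025 with 30 participants, it rejects in 28% / 92% (equal), 22% / 82% (graded) and 8% / 34% (one arm only). It does better than separate contrasts under equal gains and much worse if only one High arm works. Choosing it would be defensible, but it too is not stated.

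**Conclusion.** The point holds, and should be fixed, as a gap in pre-specification: for the cognitive composites, no stated contrast involves Low-C, and no follow-up contrast of any kind covers +6 months. The text alone establishes this. The size depends on assumptions that the documents do not settle: ρ, 10 per arm, .025 for the contrasts, and the gate. Under these the loss is greatest with equal gains and almost nil if only one High arm differs, although in that case too the named contrast answers a different question.

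Two further readings go beyond the documents. One is that Low-C or +6 months is left out of the cognitive analysis; both are in the interaction tests. The other is that imaging has the same gap; Aim 2 is stated against Low-C and has planned comparisons. How the A–B and A–C tests share alpha is a separate matter and no part of this point.

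**What to change.** Replace the sentence on pairwise contrasts in the cognitive outcomes section with planned contrasts of change for High-C versus Low-C and High-C+ versus Low-C, keeping High-C+ versus High-C. Apply them to A-to-B and to A-to-C, on the primary and the secondary composite. Test each at .025 only after the interaction for that outcome and time point is significant at .025. Report estimates and confidence intervals for both Low-C contrasts whether or not the interaction is significant.

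The cost is a change of wording. No new data are needed, and the interaction and the existing contrast both stay. The change does not create power. With 30 participants, gated High-C versus Low-C rejects in only 15% / 78% with equal gains and 6% / 34% if gains are graded. A 97.5% interval for a Low-C contrast has half-width t(.9875, 27)·√(2/10) = 2.373·.447 ≈ 1.06 change-score SD. The estimates would mainly inform the larger trial.

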Arm 1: Low Attentional Control Group (Low-C). Low attentional control training using an n-back simulation game (*Birdwatch*), requiring predictable shifts of cued-attention. Arm 2: High Attentional Control Group (High-C). High attentional control training using the *Birdwatch* simulation game, requiring unpredictable shifts of cued-attention. Arm 3: Highest Attentional Control Group (High-C+). This arm uses a commercial strategy video game for training (*Sushi Chef*), rather than the experimenter-developed simulation games proposed in the other two arms. Additionally, a *comparison group of younger adults (YA)* will undergo pre-screening, mock scan, and MRI scan sessions (but no training). All older participants will undergo 3 behavioral assessment sessions, each lasting a maximum of 3.5 hours, in the PI's lab. These assessments will be conducted at baseline, immediately post-training and 6 months after completion of training. All older adults will also undergo 2 neuroimaging assessments, one at baseline, and another at immediate post-training. There will no more than 5-day difference between the MRI scan and the respective behavioral assessment at either baseline or at immediate post-training.

The training period will last for 19 h over 8 weeks, and will include both in-lab and at-home training on a device provided to the participant. All training will be administered individually to the participant, not in a group. Fig. 5 and Fig. 6 show the computerized games used in the three training arms.

***Screening and Randomization.*** In this individually randomized trial, all interested participants will first be prescreened and will undergo a Mock Scan session to determine their eligibility to participate in the study. Participants will be consented to screening for eligibility. In order to exclude participants with memory-related disorders, primarily MCI and AD, participants will be required to have both a Mini-mental Status Examination (MMSE) score of 26 or greater, and a

Montreal Cognitive Assessment (MoCA) score of 24 or greater. A composite of these two standardized scores will comprise an index of *cognitive frailty*. The cutoff scores are conservative and should screen out most cases of MCI, although we acknowledge that some early stage MCI individuals could still be included. Additionally, brain scans will be screened by a neuroradiologist if a pathology is suspected.

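### The frailty analysis names only High-C vs High-C+, so it cannot show that frailer participants do better on High-C than on Low-C

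*Combined protocol and SAP*

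**What the plan says.** In the Data Analysis Plan, the paragraph on additional analyses at the end of the cognitive outcomes section says it will examine how frailty "interacts with training difficulty (High-C vs. High-C+) and extent of transfer". The predictions follow. Frailer adults "will benefit most from moderate attentional control training (High-C"). For fitter participants the plan expects High-C+ to be the best arm.

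Three other places bear on this:

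- The Brief Summary states the expectation without limiting it to two arms: "We also expect cognitive frailty to interact with the extent to which attentional control is trained".
- The Study Design overview sets the comparator: "the goal is to compare high attentional control trainings (High-C and High-C+) to low attentional control training (Low-C").
- The main cognitive analysis is a "repeated measures ANOVA, with Training Arms (3: Low-C, High-C, High-C+) as a between-subject factor".

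Frailty is built from the screening MMSE and MoCA (Study Design, Screening and Randomization): "A composite of these two standardized scores will comprise an index of" cognitive frailty. No model, significance level or power is given for the frailty analysis, and no section describes a frailty analysis that includes Low-C.

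**The concern.** The prediction for frailer adults is a superlative about a middle option. Of the three levels of attentional control, High-C is the middle one, with Low-C below it and High-C+ above. To say that frailer people do best in the middle, High-C has to be compared with both neighbours. The plan names only the comparison with the level above.

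The missing comparison matters on the plan's own reasoning. If greater frailty means less plasticity and less profit from the hardest training, the same logic could make Low-C the best arm for the frailest participants. Low-C and High-C also share the Birdwatch game, whereas High-C+ uses Sushi Chef (Study Design, Experimental Design). High-C vs Low-C is therefore the only frailty comparison that holds the game constant.

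The Sample Size Justification describes this study as the first phase of a larger trial. A claim about which training suits frailer adults could be carried into that trial without the comparison it depends on.

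**Working it through.** **1. The plan's own power figures.** The documents give none for the frailty analysis, so the check starts from the Training Arm x Assessment interaction in the Sample Size Justification. Inputs are f=.16, alpha .05, 3 arms and m=2 assessments. The correlation between assessments, rho, is not stated; .5 is assumed. The noncentrality is lambda = f² x N x m/(1-rho), with df 2 and N-3.

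- N=144: lambda = .0256 x 144 x 2/.5 = 14.75, df 2 and 141, power 93.5% (stated: above 93%).
- N=117: lambda = .0256 x 117 x 2/.5 = 11.98, df 2 and 114, power 87.4% (stated: above 87%).

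Both figures reproduce, so rho=.5 is a reasonable working value.

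**2. What the two-arm contrast can identify.** Score frailty z so that higher means frailer, and write the mean gain in an arm as a + b·z. The High-C vs High-C+ contrast estimates b(High-C) - b(High-C+), and the Low-C parameters do not enter it. Take assumed gains, in residual SD:

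| Arm | a | b | Gain at z=+1, case 1 | Gain at z=+1, case 2 |
|---|---|---|---|---|
| Low-C | 0 (case 1); .5 (case 2) | 0 (case 1); .5 (case 2) | 0.0 | 1.0 |
| High-C | .5 | 0 | 0.5 | 0.5 |
| High-C+ | .5 | -.5 | 0.0 | 0.0 |

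In both cases the two-arm slope difference is 0-(-.5) = .5 in favour of High-C among the frail. In case 1 High-C is the best arm for them. In case 2 Low-C is, by 1.0-0.5 = 0.5 residual SD. The named contrast cannot tell the two cases apart.

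**3. Whether leaving out Low-C costs precision.** Assume equal arms of n and an alpha of .05 two-sided. In units of residual SD per SD of frailty, the SE of the slope difference is sqrt(2/(n-1)). At n=10 this is sqrt(2/9) = .471. Error df are 20-4 = 16 with two arms and 30-6 = 24 with three. The slope difference detectable with 80% power (noncentral t) is:

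| Total N | Two arms | Three arms |
|---|---|---|
| 30 | 1.41 | 1.38 |
| 51 | 1.02 | 1.01 |
| 144 | 0.584 | 0.582 |

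In 300 simulated trials of 10 per arm, the High-C vs High-C+ slope estimate was identical with and without Low-C, apart from rounding error. The mean SE was .519 with two arms and .523 with three.

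**4. What the three-arm analysis can deliver.** For the omnibus Arm x frailty x Assessment test at N=30 and f=.16, lambda = .0256 x 30 x 2/.5 = 3.07 with df 2 and 24, giving 29% power. With rho=.3 lambda is 2.19 and power 22%; with rho=.7 lambda is 5.12 and power 46%. At rho=.5, power is 49% at N=51 and 94% at N=144. At the pilot effect f=.35 it is 91% at N=30.

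The quantity that answers the prediction is the High-C minus Low-C difference in gain at high frailty. At z=+1 its SE is sqrt(2 x (1/n + 1/(n-1))), which at n=10 is sqrt(2 x (.100+.111)) = .65 residual SD. The 95% half-width is 2.064 x .65 = 1.34 residual SD.

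**The case against.** The best defence is that the core of the prediction is the crossover between High-C and High-C+, and the named contrast tests it directly. That stands: a reader might infer that the frailty hypothesis is untestable as planned, and it is not. Only the ranking against Low-C is lost.

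A second defence is that no model is written out. Just before this paragraph, the plan fits a three-arm ANOVA and then singles out High-C vs High-C+ as its pairwise contrast. The frailty text may likewise name one contrast within a three-arm model. That is possible, although elsewhere the plan lists all three arms when it means three. On either reading, no High-C vs Low-C contrast across frailty is specified.

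Three stronger readings are tempting, and the documents do not support them:

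- *A third of the sample is discarded.* Exclusion of Low-C is inferred from a parenthesis, and no allocation ratio is stated. The year-1 targets of 10:10:6 would put Low-C at 10/26 = 38%.
- *Precision suffers through lost error df.* The rise from 16 to 24 moves the detectable slope difference only from 1.41 to 1.38.
- *Without Low-C, moderation is confounded with practice effects or regression to the mean.* Both arms are randomised, so frailty-related effects common to them cancel in the slope difference. Low-C is also active adaptive training and would not isolate those effects.

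Finally, this is an additional analysis outside the two ANOVAs tested at .025, and adding Low-C does not cure its low power at N=30. That is true. It argues for an exploratory label and interval estimates, not for omitting the comparison.

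**Conclusion.** The concern holds in a limited form. The planned contrast can support a statement about High-C relative to High-C+ across frailty. It cannot support the statement that frailer participants benefit *most* from High-C, because High-C is not compared with Low-C.

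The size of the problem lies in what may be concluded: the same two-arm result is compatible with Low-C being the worst or the best arm for frail participants. Precision for the named contrast is essentially unaffected. The numerical results assume equal arms, a two-sided alpha of .05 and, for power, a correlation of .5 between assessments. The logical point needs none of these. It is a low-cost improvement to an additional analysis and does not touch the primary or secondary ANOVAs.

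**What to change.** Specify the frailty analysis as Training Arm (Low-C, High-C, High-C+) x continuous frailty x Assessment. With two assessments this is equivalent to Arm x frailty on the change score. Report:

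1. the frailty slope in each arm with its confidence interval;
2. the High-C vs High-C+ and High-C vs Low-C slope differences;
3. the estimated High-C vs Low-C difference in gain at a stated high value of frailty, within the range that the screening cutoffs allow.

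State the direction in which frailty is scored, and label the analysis exploratory; the plan now calls it only additional.

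If Low-C is not added, reword the prediction and restrict any conclusion to High-C relative to High-C+.

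The cost is a change of wording. MMSE and MoCA are taken at screening, and the outcomes are already planned for all older participants. The downside is one more contrast in an analysis that will be imprecise at N=30, so the write-up should rest on the intervals rather than on significance.
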